APPENDIX V: PATIENT INSTRUCTIONS FOR TREATING DIARRHEA

Be aware of your/your child's bowel movements. At the first sign they become softer than usual or if your child has any increase in the number of bowel movements over what is normal for him/her, then you/your child should begin taking loperamide (Imodium). **If he/she does not start taking the loperamide right away, the diarrhea may become severe and last several days or require hospitalization.**

Please follow these directions carefully, using dosing guidelines below:

Take _____ loperamide at the first sign of diarrhea.

Continue taking _____ loperamide every _____ hours until your normal pattern of bowel movements returns. Repeat the same doses and frequency if the diarrhea returns.

Do not give more than _____ of loperamide in a 24 hour period.

Please call your doctor if you have any questions about taking loperamide, if your child's diarrhea is not under control after two days, or if he/she is feeling extremely weak, lightheaded, or dizzy.

Make an extra effort to give your child lots of fluids (several glasses of pedialyte, fruit juices, soda, soup, etc.) while your child is participating in this study.

Side effects may include tiredness, drowsiness, or dizziness. If your child experiences these side effects, or if your child is urinating less frequently than usual, please contact your child's physician.

Do not give your child any laxatives without consulting with his/her physician.

Loperamide dosing guidelines:

Loperamide is usually supplied in the following forms: 1 teaspoon = 1mg; 1 caplet = 2mg

Maximum dose of loperamide per day: < 6 years: 4 mg/day; 6-11 years: 6 mg/day; >11 years: 16 mg/day, using the non silicone-containing product.

Weight: > 43 kg: 4 teaspoons or 2 caplets (4 mg) after the first loose bowel movement, followed by 2 teaspoons or 1 caplet (2mg) every 2 hours. During the night the patient may take, 2 caplets (4mg) every 4 hours rather than 1 caplet (2mg) every 2 hours.

Weight: 30kg – 43kg: 2 teaspoons or 1 caplet (2mg) after the first loose bowel movement followed by 1 teaspoon or one-half caplet (1 mg) every 2 hours. During the night the patient may take, 1 caplet (2 mg) every 4 hours rather than one-half caplet every 2 hours.

Weight: 20kg – < 30kg: 2 teaspoons or 1 caplet (2mg) after the first loose bowel movement followed by 1 teaspoon or one-half caplet (1mg) every 3 hours. During the night, the patient may take 1 caplet (2mg) every 4 hours rather than one-half caplet every 3 hours.

Weight: 13kg - < 20kg: 1 teaspoon (1mg) after the first loose bowel movement followed by 1 teaspoon (1mg) every 3 hours. During the night, the patient may take 1 teaspoon (1 mg) every 4 hours rather than every 3 hours.

Weight: < 13kg: Half teaspoon (0.5mg) after the first loose bowel movement followed by half teaspoon every 3 hours. During the night, the patient may take half teaspoon (0.5mg) every 4 hours rather than every 3 hours.

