5.4 Treatment of Irinotecan-Associated Diarrhea

Irinotecan-associated diarrhea can be profuse and can occur either early (minutes to hours) or late (days) in the treatment schedule. Early diarrhea results from cholinergic stimulation, while late diarrhea relates to bacterial processing of irinotecan metabolites.

Early diarrhea: Patients who have the onset of diarrhea during the irinotecan infusion or in the hours following the completion of an irinotecan infusion should receive atropine (suggested dose 0.01 mg/kg IV, maximum dose 0.4 mg). Early onset diarrhea is usually accompanied by cholinergic manifestations (diaphoresis and abdominal cramping). Since irinotecan is being administered on a prolonged schedule (daily x 5), it may be difficult to distinguish early versus late diarrhea. If a patient with presumed early diarrhea does not improve with administration of atropine, they should be instructed to begin treatment for late diarrhea. Patients with suspected early diarrhea should also have the duration of subsequent Irinotecan infusions prolonged to 90 minutes.

Late diarrhea (more than 24 hours after irinotecan administration): Patients will be given loperamide for late diarrhea based on body weight according to the following chart. Each family will be instructed to have loperamide available and begin treatment at the first episode of poorly formed or loose stools or the earliest onset of bowel movements more frequent than normally expected for the patient. Families should be given the handout in Appendix V. Patients will also be instructed to contact their physician if any diarrhea occurs.

Maximum dose of loperamide per day: < 6 years: 4mg/day; 6-11 years: 6mg/day; >11 years: 16 mg/day, using the non silicone-containing product.	
Weight: > 43 kg:	4 teaspoons or 2 caplets (4 mg) after the first loose bowel movement, followed by 2 teaspoons or 1 caplet (2mg) every 2 hours. During the night the patient may take, 2 caplets (4mg) every 4 hours rather than 1 caplet (2mg) every 2 hours.
Weight: 30kg – 43kg:	2 teaspoons or 1 caplet (2mg) after the first loose bowel movement followed by 1 teaspoon or one-half caplet (1 mg) every 2 hours. During the night the patient may take, 1 caplet (2 mg) every 4 hours rather than one-half caplet every 2 hours.

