Weight: 20kg – < 30kg:	2 teaspoons or 1 caplet (2mg) after the first loose bowel movement followed by 1 teaspoon or one-half caplet (1mg) every 3 hours. During the night, the patient may take 1 caplet (2mg) every 4 hours rather than one-half caplet every 3 hours.
Weight: 13kg - < 20kg:	1 teaspoon (1mg) after the first loose bowel movement followed by 1 teaspoon (1mg) every 3 hours. During the night, the patient may take 1 teaspoon (1 mg) every 4 hours rather than every 3 hours.
Weight: < 13kg:	Half teaspoon (0.5mg) after the first loose bowel movement followed by half teaspoon every 3 hours. During the night, the patient may take half teaspoon (0.5mg) every 4 hours rather than every 3 hours.

[figure not shown]
If there is failure of loperamide to control severe diarrhea after 24 hours of use, patients should be considered for treatment with **octreotide** (Sandostatin™) at the dose of **10 micrograms/kg/dose** subcutaneously every 12 hours x 3 days.

Patients receiving prolonged exposure to antibiotics (i.e., cefixime) who develop diarrhea should have stool samples evaluated for *C difficile* toxin, as this is a potentially treatable cause of diarrhea. If patients have fever with diarrhea, or bloody diarrhea, evaluation of stools for bacterial culture should also be performed.

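### The family diarrhea handout (Appendix V) omits Section 5.4's instruction to contact the physician for any diarrhea and prints two days as its only duration-based reason to call

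*Combined protocol and SAP*

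**What the plan says.** Section 5.4 (Treatment of Irinotecan-Associated Diarrhea), in its paragraph on late diarrhea, has families keep loperamide at hand and begin it at the first loose stool. It then says: "Families should be given the handout in Appendix V". The next sentence is the section's only instruction to patients about contacting the site: "Patients will also be instructed to contact their physician if any diarrhea occurs".

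The section goes on to clinician steps. Octreotide is to be considered "If there is failure of loperamide to control severe diarrhea after 24 hours of use". Patients with prolonged antibiotic exposure, with cefixime as the example, "who develop diarrhea should have stool samples evaluated for" C. difficile toxin. Stool culture is added for fever or blood.

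Appendix V tells the family to start loperamide promptly ("At the first sign they become softer than usual", or at any increase in frequency). It leaves a blank for the maximum amount "of loperamide in a 24 hour period". Its reasons to call are:

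- questions about loperamide;
- the child's "diarrhea is not under control after two days";
- extreme weakness, lightheadedness or dizziness;
- loperamide side effects (tiredness, drowsiness, dizziness);
- the child "urinating less frequently than usual, please contact your child's physician".

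It contains no instruction to call for any diarrhea.

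**The concern.** The handout is the page a family has at home when diarrhea starts, and it asks to be followed carefully. A printed two-day threshold implies that shorter diarrhea, without the listed symptoms, needs no call. Section 5.4 intends contact whenever diarrhea occurs.

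The octreotide and C. difficile steps can begin only once the site knows about the diarrhea. Late diarrhea, which Section 5.4 defines as more than 24 hours after irinotecan, can fall outside the infusion visits on days 1 to 5. The stake is therefore a possible delay in managing a known toxicity in children, not the trial's inference.

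**Working it through.** The plan gives no figure to reproduce, so the check sets the two texts side by side.

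| Item | Section 5.4 | Appendix V |
|---|---|---|
| Start of loperamide | First loose stool; no prior call required | First softening or increased frequency; no prior call required |
| Call for any diarrhea | Yes | Not printed |
| Duration-based call trigger | None needed, since contact is at onset | Two days without control |
| Symptom-based call triggers | None stated for families | Weakness, lightheadedness, dizziness, tiredness, drowsiness, reduced urination |
| Severe diarrhea after 24 h of loperamide | Clinician considers octreotide | Not mentioned |
| Fever or blood | Clinician adds stool culture | Not mentioned |

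**Step 1: where they differ on contact.** The first row agrees. The mismatch is in the second and third rows: Section 5.4 has contact at onset, and the sheet has it at two days unless another prompt applies.

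**Step 2: size of the gap.** Two days = 2 × 24 h = 48 h. Contact at onset is 0 h. Gap = 48 h − 0 h = 48 h at most. This counts the sheet's two days from onset; the sheet does not say when they begin.

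**Step 3: who could be affected.** Section 4.2.5 requires cephalosporin prophylaxis for all phase 2 and oral solution patients, from day −1 (two days before irinotecan) to day 8. That is days −1 and 0 plus days 1 to 8: 2 + 8 = 10 days of each 21-day cycle. Section 5.4 names cefixime as its example of prolonged exposure, so the C. difficile step can apply to any of these patients who develops diarrhea.

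**Step 4: other ways the site would learn of it.** The Section 7.1 table schedules weekly exams and chemistries and twice-weekly blood counts in cycle 1. From cycle 2 the exam and chemistries are at the start of each cycle, with weekly counts. Visits may bring diarrhea to light, particularly in cycle 1, but none is timed to its onset.

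**The case against.** The strongest reply is that Section 5.4 already requires the contact instruction in addition to the handout, so a family can follow both. The sheet never says to wait, and its symptom prompts would bring many sick children to attention before two days. Consent pages were removed before review, so other written advice may exist. All of this stands and limits the harm. It does not remove the mismatch, because the sheet still prints a later threshold than the instruction it accompanies.

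A reader might infer more than the documents support:

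- **That starting loperamide at home without a call departs from Section 5.4.** It does not; Section 5.4 has the same prompt start and requires no prior call.
- **That the sheet is 24 hours late against the octreotide rule (48 h − 24 h).** This compares unlike things. The 24-hour point is a clinician step for severe diarrhea only, while the two-day trigger is a family prompt for any uncontrolled diarrhea. The subtraction also assumes that both clocks start at the first loperamide dose. Consideration of octreotide could be delayed, but 24 hours is not a measured conflict.
- **That missing fever and blood prompts are an inconsistency.** Section 5.4 gives families no such call rule either.
- **That reported diarrhea rates size the harm.** Section 2.11 reports grade 3 diarrhea in 3 of 6 patients at dose level 1, before prophylaxis was mandatory. Section 2.12 lists no diarrhea among the first-course DLTs in the 6 + 6 + 4 = 16 patients at levels 1B, 2B and 3B, but Section 4.4 exempts grade 3 diarrhea lasting under 72 hours. Neither figure measures delayed contact or its consequences.

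**Conclusion.** The concern holds as a mismatch between Section 5.4 and the sheet it tells sites to hand out. On the printed text, contact could come up to two days later than Section 5.4 intends. This applies to a family that relies on the sheet over the separate instruction and whose child has none of the sheet's other prompts. How many families that describes cannot be estimated from the documents.

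The conclusion assumes that the sheet is used as printed and that its two days run from onset. It does not assume that families are never told to call for any diarrhea. It does not extend to DLT classification, endpoints or error rates; nothing in the documents links the handout wording to any of them. It is a limited patient-safety wording fault, worth correcting because the correction is simple.

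**What to change.** In Appendix V, replace the two-day trigger with an instruction to call the doctor if any diarrhea occurs. Keep the immediate loperamide start, the dosing text and the existing symptom prompts. Section 5.4 needs no change.

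As an optional safety addition that goes beyond reconciling the two texts, the sheet could tell families to call again at once if severe diarrhea is not controlled after 24 hours of loperamide, or if there is fever or blood in the stool. The sponsor's clinicians should set that wording.

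The cost is a short revision to one handout and somewhat more phone calls to sites.

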APPENDIX VI: BLOOD VOLUME SUMMARY FOR INVESTIGATIONAL STUDIES

Summary of Research Blood Samples: Blood volumes below are maximum values.

For patients with a weight below the minimum required to tolerate all blood draws requested for correlative studies , please consult with study chair to determine prioritization of samples.

Course	Day	Sample Time Points (based on timing of MLN8237 dosing) *	MLN8237 Pharmacokinetics	Irinotecan Pharmacokinetics **	UGT 1A1 Polymorphisms	Total
1	1	(Pre-dose)0 hr	3mL	2mL	10mL	15mL
	4	(Pre-dose) 0 hr	3mL	2mL	----	5mL
		0.5hr	3mL	----	----	3mL
		1 hr	3mL	----	----	3mL
		2 hr	3mL	2mL	----	5mL
		3 hr	3mL	2mL	----	5mL
		4 hr	3mL	2mL	----	5mL
		7hr	3mL	2mL	----	5mL
	5	Pre-day 5 dose of MLN8237	3mL	2mL	----	5mL
						TOTAL : 51 mL

*Refer to sections 8.1.2 and 8.2.2 for further clarification of sample time points.

**See section 8.2.1 for restrictions if patient has a central line.

APPENDIX VII RESPONSE CRITERIA VERSION 1

These criteria are to be used for patients enrolled prior to Amendment #5.

Response Criteria for CT/MRI Lesions

For CT/MRI lesions, this study will use the definitions of measurable disease from the Response Evaluation Criteria In Solid Tumors (RECIST) from the National Cancer Institute. Overall response for each patient will be defined as outlined in Section 11.4.

Definition of Measurable (Evaluable) Disease on CT/MRI scan

The presence of at least one lesion that can be accurately measured in at least one dimension with the longest diameter at least 20 mm. With spiral CT scan, lesions must be at least 10 mm. The investigator will identify up to 10 measurable target lesions to be followed for response. Note that bone lesions will be considered as non-target lesions for evaluation of CT/MRI response since they will be evaluated with MIBG scans.

Serial measurements of lesions are to be done with CT or MRI. The same method of assessment used to characterize each identified and reported lesion at baseline should be used during follow-up.

The sum of the longest diameter (LD) for all target lesions will be calculated and reported as the **disease measurement**. The response of the CT/MRI lesions will be defined as outlined below:

Complete Response (CR)

Disappearance of all target and non-target CT/MRI lesions.

Very Good Partial Response (VGPR)

Greater than 90% decrease of the disease measurement for CT/MRI lesions, taking as reference the disease measurement done to confirm measurable disease at study entry. Non-target CT/MRI lesions stable to smaller in size.

Partial Response (PR)

At least a 30% decrease in the disease measurement for CT/MRI lesions, taking as reference the disease measurement done to confirm measurable disease at study entry. Non-target CT/MRI lesions stable to smaller in size.

Progressive Disease (PD)

At least a 20% increase in the disease measurement, taking as reference the smallest disease measurement since the treatment started, OR a new site of tumor. Non-target CT/MRI lesions stable, smaller, or increased in size.

Stable disease (SD)

Neither sufficient shrinkage to qualify for PR nor sufficient increase to qualify for PD taking as reference the smallest disease measurement since the treatment started. No new sites of disease.

Response Criteria for Morphologic Bone Marrow Disease

Only those patients with morphologic evidence of neuroblastoma by routine H and E staining (NSE staining only is not evaluable) will be evaluable to assess bone marrow response.

Complete Response

Will be defined as no tumor cells detectable by routine morphology on two subsequent bilateral bone marrow aspirates and biopsies done at least three weeks apart after study entry.

Progressive Disease will be defined as:

Tumor seen on morphology on two consecutive bone marrows done at least three weeks apart in patients who had NO tumor in bone marrow at study entry. (Note: Patient may be declared as progressive disease in bone marrow after only one diagnostic bone marrow at the discretion of the treating physician after discussion with the study chair.)

Patients who enter study with bone marrow tumor by morphology will be considered to have progressive disease if there is a minimum of 25% tumor in the marrow by morphology **AND** a doubling in the amount of tumor in the marrow compared to the level present at study entry. (For example, a patient entering with 5% tumor in marrow by morphology must increase to $\geq 25\%$ tumor to have PD; a patient entering with 30% tumor must increase to $\geq 60\%$ tumor).

Stable Disease

Will be defined as persistence of an amount of tumor in the bone marrow by morphology that does not meet criteria for either complete response or progressive disease. Patients who clear morphologic tumor but have immunocytologic tumor will be called SD.

Response Criteria for MIBG Positive Lesions

All patients will be evaluable for MIBG response following the first course of therapy. Patients with persistent MIBG-positive disease after the first course will also be evaluable for MIBG response following the second course of therapy.

Definition of MIBG Response

The following criteria will be used to report MIBG response by the treating institution on the end of course report forms:

[figure not shown]
- a. Complete response = complete resolution of all MIBG positive lesions
- a. Partial response = resolution of at least one MIBG positive lesion, with persistence of other MIBG positive lesions.
- b. Stable disease = no change in MIBG scan in number of positive lesions (includes patients who have same number of positive lesions but decreased intensity)
- c. Progressive disease = Development of new MIBG positive lesions

Assessment of MIBG Response

The response of MIBG lesions will be assessed on central review using the Curie scale as outlined below.[22] Central review responses will be used to assess efficacy for study endpoint.

NOTE: This scoring is NOT required to be done by the treating institution for their end of course response assessments.

The body is divided into 9 anatomic sectors for osteomedullary lesions, with a 10th general sector allocated for any extra-osseous lesions. In each region, the lesions are scored as follows. The **absolute extension score** is graded as: 0 = no site per segment, 1 = 1 site per segment, 2 = more than one site per segment, 3 = massive involvement ($>50\%$ of the segment). The absolute score is obtained by adding the score of all the segments. See diagram of sectors below:

The **relative score** is calculated by dividing the absolute score at each time by the corresponding pre-treatment overall score. The relative score of each patient is calculated at each response assessment and classified as below:

- a. Complete response: all areas of uptake on MIBG scan completely resolved.
- b. Partial response: Relative score ≥ 0.1 (lesions almost disappeared) to < 0.5 (lesions strongly reduced),
- c. Stable disease: Relative score > 0.5 (lesions weakly but significantly reduced) to < 1 (lesions not reduced).
- d. Progressive disease: New lesions on MIBG scan.

Definition of Overall Response for Each Patient

The **International Neuroblastoma Response Criteria** were developed to define responses in patients being treated with frontline therapy from diagnosis.[23] These criteria were utilized as a basis for the following response criteria, which integrate response at all sites defined as measurable in this study, including CT/MRI lesions which meet RECIST criteria, MIBG positive lesions, and bone marrow disease. These criteria will be used to define the overall response for each patient.

Complete Response (CR)

Disappearance of all target lesions. No evidence of tumor at any site (chest, abdomen, liver, bone, bone marrow, nodes, etc.), and HVA/VMA normal.

Very Good Partial Response (VGPR)

Greater than 90% decrease of the disease measurement for CT/MRI target lesions, taking as reference the disease measurement done to confirm measurable disease in target lesions at study entry; all pre-existing bone lesions with CR by MIBG; MIBG scan can be SD or CR in soft tissue lesions corresponding to lesions on CT/MRI. CR in bone marrow. No new sites of tumor. HVA/VMA normal.

Partial Response (PR)

At least a 30% decrease in the disease measurement for CT/MRI target lesions, taking as reference the disease measurement done to confirm measurable disease in target lesions at study entry. Bone marrow with CR. MIBG with either PR/CR in bone lesions; MIBG may be SD or CR in soft tissue lesions corresponding to lesions on CT/MRI. HVA/VMA may still be elevated.

Progressive Disease (PD)

Any one of the following:

- a. At least a 20% increase in the disease measurement for CT/MRI target lesions, taking as reference the smallest disease measurement recorded since the start of treatment.
- b. Appearance of one or more new lesions or new sites of tumor.
- c. PD as defined above for either bone marrow or MIBG lesions.

Stable disease (SD)

The patient will be classified as stable disease for overall response if there is stable disease by either CT/MRI lesion, bone marrow, or MIBG criteria. No new lesions; no new sites of disease.

Mixed response (MR)

The patient will be classified as mixed response for overall response if there is complete response, partial response, and/or very good partial response at a minimum of one site (i.e. CT, MIBG, and/or bone marrow), with stable disease at all other sites and any value of catecholamines.

The overall response as assessed at any particular time point based on the various disease sites is summarized in the table below.

Overall Response Assignment

Response by individual site				Overall response
CT/MRI lesions	MIBG lesions	Bone marrow	Catechols	
PD	Any	Any	Any	PD
Any	PD	Any	Any	PD
Any	Any	PD	Any	PD
CR	CR	CR	Normal	CR
			Normal	CR
VGPR	CR in bone lesions ; May have SD/CR in soft tissue sites corresponding to lesions on CT/MRI	CR	Normal	VGPR
PR	PR/CR in bone lesions; May have SD/CR in soft tissue sites corresponding to lesions on CT/MRI	CR	Any	PR
SD	SD	SD	Any	SD
SD/PR/VGPR/CR	SD	SD/CR	Any	SD
SD/PR/VGPR/CR	SD/PR/CR	SD	Any	SD

Mixed response: CR, PR and/or VGPR at minimum of one site, with SD at all other sites; any catecholamines

